#### Psychometrics Testing:

Structured Clinical Interview for DSM-IV (SCID) (Michael et al., 2002) SC rated; the SCID will be administered to all participants for screening purposes for entry into the study. This is a structured interview that allows for making diagnoses in accordance with DSM-IV. The interview takes approximately 30 minutes, depending on the pathology of the subject. If a SCID has been completed by study team within 1 year prior to enrollment and no change has occurred in mood/condition of participant, the previous SCID administered can be used as part of this study instead of duplication the diagnostic interview.

Bipolar Inventory of Symptoms Scale (BISS) (Bowden et al. 2007, Gonzale et al. 2008,). The Bipolar Inventory of Symptoms Scale (BISS), a 44-item scale designed to encompass the spectrum of behavioral disturbances in Bipolar Disorder. The BISS total score and depression and mania subscales were compared to the Young Mania Rating Scale (YMRS), the Montgomery Asberg Depression Rating Scale (MADRS) and the Global Assessment of Functioning Scale (GAF). The BISS has adequate reliability, concurrent validity and is capable of discriminating between bipolar subtypes. It also provides a comprehensive scale to assess discrete behavioral components of Bipolar Disorder.

Clinical Global Impression Scale for Bipolar Illness (CGI-BP) (Spearing et al., 1997) Clinician Rated; The CGI as modified for bipolar illness allows for rating of degree of clinical improvement in depression, mania, and overall illness. Moreover, it addresses many of the specific criticisms leveled at the CGI relating to the types of ratings, technical and scaling problems, definition of time domain of the rating, and confounding of clinical response with tolerability and side effects. Index II of this instrument assess "change from preceding phase" of bipolar illness, rates of 1 (very much improved) or 2 (much improved) in the mania, depression and overall bipolar illness ratings will be considered the outcome measure of treatment response. Part "E" of the CGI-BD will be used to record side effects reported by the participant as well as their severity.

#### Mood Check Application (Utley 2015)

MoodCheck™ is a mobile application with the purpose of mood and medication monitoring designed for patients with depression or bipolar disorder. The platform is designed to engage patients in managing/quantifying symptoms and monitoring change associated with treatment intervention. The app prompts users to enter their mood each day at a preset time that can be changed by the user for a “push notification” or alarm. Data takes less than 30 seconds to input, making it simple for patients to use. App users can automate reports and graphs to be sent to their mental health provider, allowing the provider and clinical team to analyze how the patient feels their medication dosage or medication brand is impacting their mood, while allowing a tracking mechanism for clinical trials, research studies, and overall patient care success.

#### WHO-5 Wellbeing index (Wu 2014) (Bech 1998)

The WHO-5 Well-being Index is a short, self-administered questionnaire covering 5 positively worded items, which are related to positive mood (good spirits, relaxation), vitality (being active and waking up fresh and rested), and general interests (being interested in things), and has proved to be a reliable measure of emotional functioning. Each of the five items is rated on a 6-point Likert scale from 0 (= not present) to 5 (= constantly present). The lower the total score is, the more severe the depression, poor physical health, and psychological health are. The higher the total score, the better the physical and psychological health. An answered score of 1 or 0 on any of these items means that it may be helpful to consult with a counseling professional. A score of 13 or lower suggests further investigation into possible symptoms of depression.

Columbia-Suicide Severity Rating Scale (C-SSRS), (Posner et al. 2008) Clinician Rated; 21 -item interviewer administered rating scale that measures current intensity of suicidal ideation and will be measured at baseline at each visit.

#### Actigraph™

100 subjects (50 from Mayo Clinic and 50 from Lindner Center of HOPE) who are enrolled in this study will be asked to participate in a sub-study using Actigraphs (ActiGraph wGT3X-BT) to measure circadian activity and sleep patterns for a period of 16 weeks. The subject's decision to participate in this sub-study is completely voluntary and does not affect participation in the FLAME study.

Study visits are specified in Table 1.

Table 1. Study visits.

		Bipolar I or II Depressed Participants																									
		Screening	Enrollment		Week 1		Week 2		Week 3		Week 4		Week 6		Week 8		Week 10		Week 12		Week 14		Week 16				
Procedure	V*	V*1	V 2	V 3	Telephone Call	V4	Telephone Call	V5	Telephone Call	V6	Telephone Call	V7	Telephone Call	V8	Telephone Call	V9	Telephone Call	V10	Telephone Call	V11	Telephone Call	V12	Telephone Call	V13	Telephone Call		
Consent	X																										
Vital Signs		X	X	X			X		X		X													X			
Drug Initiation		X																									
Blood Draw		X		X		X																			X		
Urine pregnancy		X																									
Toxicology Urine		X																									
BISS	X	X	X	X			X		X		X														X		
CGI-BP†		X	X	X			X		X		X														X		
C-SSRS	X	X	X	X			X		X		X														X		
MoodCheck		x	x	x	x		x	x	x	x	x	x												x	x		
WHO-5		X																								X	
Compliance medication count			X	X			X		X		X														X		
Actigraph			X																							X	
Treatment Adherence Form				X	X			X		X		X													X		

\*Visit (V). \*\* Only participants who accept to participate in biomarker epigenetic and metabolomic/proteomic studies. †Drug adverse events to treatment for pharmacogenomics phenotype are also recorded in the CGI-BP.  
The visit window will be +/- 7 days from the scheduled date,

**Study Medication**

1. The study PI or Co-I will be in charge of medication administration, dosage and changes at baseline and follow-up visits:
2. Bipolar I, Bipolar II, or schizoaffective disorder depressed
3. Dosing for adults as monotherapy or on lithium or antipsychotic: LTG 25 mg daily x 2 weeks, 50 mg daily x 2 weeks, 100 mg daily x 2 weeks, 200 mg (100 mg bid) x 4 weeks. If patient still has at least mild depressive symptoms (CGI  $\geq$  3) the dose can be increased to 300 mg daily for 2 weeks and 400 mg for 4 weeks. Dose will be held for treatment response and can be reduced for side effect.
4. Fluoxetine dosing: 20mg for month 1, 40mg for month 2, and if still depressed (CGI  $\geq$  3) 60mg for month 3 and 4. Lower doses of fluoxetine will be prescribed for those with side effects. For known 2D6 Poor Metabolizers, fluoxetine will not be dosed > 40mg.
5. Valproate Lamotrigine Titration: 25mg (half tablet) daily for week 1 and week 2, 25mg daily for week 3 and week 4, 50mg daily for week 5-6, 100mg daily for week 7-10, and 100mg daily for week 11-16.

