### **Inclusion Criteria:**

1. Adult participants, age 18-65.
2. Outpatients or inpatients with a diagnosis of bipolar I, II or schizoaffective bipolar disorder, depressed phase, non-psychotic, (DSM-IV criteria, SCID Module A and D confirmed).

3. At least mild symptom severity of depression as defined by the Clinical Global Impression for Bipolar Disorder (CGI-BP, Spearing et al. 1997) >2
4. Antimanic mood stabilization treatment. Bipolar I participants must be on conventional mood stabilizing treatment [lithium, divalproex or valproate, or an atypical antipsychotic]. Participants with Schizoaffective Bipolar Disorder must be on an atypical antipsychotic. Participants with bipolar II disorder may pursue the FLAME Study as monotherapy.
5. Negative urine pregnancy test.
6. Participants not planning pregnancy in the near future (6 months).
7. Negative urine toxicology screen (except cannabis).
8. No evidence of clinically significant laboratory screening tests (complete blood count (CBC); electrolytes; thyroid stimulating hormone (TSH); creatinine/BUN, AST/ALT). Clinical laboratory evaluation within the last three months is acceptable.

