Based on older guidelines for dosing of lamotrigine, there were some serious side effects, which in clinical trials of bipolar and other mood disorders occurred in approximately 0.08% (0.8 per 1,000) of adults taking lamotrigine as initial monotherapy and 0.13% (1.3 per 1,000) in adults receiving lamotrigine as adjunctive therapy. These side effects can be serious and potentially life-threatening. These are mainly side effects related to the skin, and include Stevens Johnson Syndrome (a severe rash around the eyes, mouth, genital, anal, and other skin areas), toxic epidermal necrolysis (severed blistering and sloughing of the skin), angioedema (swelling under the skin), and hypersensitivity syndrome (an allergy-like reaction with fever, swollen glands, rash, blood or liver problems, and facial swelling). Almost all of the life-threatening rashes have occurred within 2 to 8 weeks after starting to take lamotrigine. However, there have been a few people who developed these rashes months after starting lamotrigine. The only known factor that has been identified to predict the risk of the occurrence or severity of lamotrigine associated rash is age; pediatric participants are at greater risk than adults. Three factors have been suggested as potential causes for an increased risk of serious rash: 1) starting at too high of a dose, 2) increasing the dose too quickly, and 3) coadministration with valproate. The risk is increased to 1 out of every 100 adults who take a combination of lamotrigine and divalproex sodium. In worldwide post-marketing experience, rare cases of rash-related death have been reported, although the numbers are too few to estimate a risk. However, these deaths occurred when using the old dose recommendations. New data would suggest that with more conservative guidelines, as noted in the Physician's Desk Reference and as being followed in this study, this risk is reduced.

Non-serious rashes also occur when taking lamotrigine; however, it is not possible to know which rashes will become severe. Thus any rash, skin discoloration, blister, or mouth sore should be reported immediately. In general, lamotrigine should be discontinued at the first sign of rash, unless the rash is clearly not drug-related. Even if one stops taking lamotrigine, a rash could become severe or permanently disabling or disfiguring. In extremely rare cases, multiorgan failure has been observed in 2

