#### 5. Product Accountability

Medication will be stored with the Mayo Clinic Pharmacy. All prescriptions will be signed by a study doctor and picked up by a member of the study team.

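### The starting dose of lamotrigine with valproate can be read as 12.5 mg or 25 mg daily, and the 25 mg reading removes the valproate reduction at the first step

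*Combined protocol and SAP*

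**What the plan says.** Study Medication in the combined protocol and SAP has two lamotrigine schedules.

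- Item 3, without valproate: "Dosing for adults as monotherapy or on lithium or antipsychotic: LTG 25 mg daily x 2 weeks, 50 mg daily x 2 weeks", followed by "100 mg daily x 2 weeks, 200 mg (100 mg bid) x 4 weeks".
- Item 5, with valproate: "25mg (half tablet) daily for week 1 and week 2, 25mg daily for week 3 and week 4", followed by "50mg daily for week 5-6, 100mg daily for week 7-10, and 100mg daily for week 11-16".

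No lamotrigine tablet strength is given in either item or elsewhere in the text supplied.

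Valproate is permitted background treatment. Inclusion criterion 4 reads: "Bipolar I participants must be on conventional mood stabilizing treatment [lithium, divalproex or valproate, or an atypical antipsychotic". The section on possible risks of the study medications lists three suggested causes of a raised risk of serious rash: "1) starting at too high of a dose, 2) increasing the dose too quickly, and 3) coadministration with valproate". The same section says that the study follows more conservative dosing guidance from an outside reference, but it does not reproduce that schedule.

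On control of dosing, Study Medication item 1 says "The study PI or Co-I will be in charge of medication administration, dosage and changes", and Product Accountability says "All prescriptions will be signed by a study doctor".

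**The concern.** The milligram figure and the half-tablet note in item 5 agree only if the tablet is 50 mg. If it is 25 mg, half of it is 12.5 mg and the printed 25 mg is wrong. A prescriber or pharmacist can reach either dose from the same line, and the two differ two-fold.

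A separate schedule for valproate only makes sense as a reduction. If the printed number is followed, the first step is not reduced at all. That would bring together two of the three factors that the protocol itself lists as suggested causes of serious rash: a high starting dose and co-administration with valproate. The protocol relies on conservative dosing to lower this risk, and the line leaves a reader unable to tell whether the first dose is conservative.

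**Working it through.** The plan gives no sample-size, power or error-rate figure on this point. The check compares the two schedules step by step under both readings.

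**Inputs** (Study Medication, items 3 and 5)

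- Without valproate: 25, 50, 100 and 200 mg daily for 2, 2, 2 and 4 weeks.
- With valproate: weeks 1-2 unclear; then 25 mg (weeks 3-4), 50 mg (weeks 5-6) and 100 mg (weeks 7-10).
- Reading A: half of a 25 mg tablet, 25 / 2 = 12.5 mg. Reading B: the printed 25 mg, which needs a tablet of 2 × 25 = 50 mg.

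**Ratio of daily doses** = dose with valproate / dose without valproate

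| Weeks | Without valproate (mg) | Reading A | Reading B |
|---|---|---|---|
| 1-2 | 25 | 12.5 / 25 = 0.5 | 25 / 25 = 1.0 |
| 3-4 | 50 | 25 / 50 = 0.5 | 25 / 50 = 0.5 |
| 5-6 | 100 | 50 / 100 = 0.5 | 50 / 100 = 0.5 |
| 7-10 | 200 | 100 / 200 = 0.5 | 100 / 200 = 0.5 |

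**Cumulative dose** = sum of daily dose × days

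| Period | Reading A (mg) | Reading B (mg) | Without valproate (mg) | A and B as a share of the last |
|---|---|---|---|---|
| Weeks 1-2 | 12.5 × 14 = 175 | 25 × 14 = 350 | 25 × 14 = 350 | 50% and 100% |
| Weeks 1-4 | 175 + 350 = 525 | 350 + 350 = 700 | 350 + 700 = 1050 | 50% and 67% |
| Weeks 1-10 | 525 + 700 + 2800 = 4025 | 700 + 700 + 2800 = 4200 | 1050 + 1400 + 5600 = 8050 | 50% and 52% |

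Under reading A every step through week 10 is halved. Under reading B the first step is the only exception. The two readings differ by 175 mg in total, all of it in the first 14 days; from week 3 the daily dose is the same.

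**What the wording adds.** Weeks 1-2 and weeks 3-4 both show 25 mg, but only weeks 1-2 carry the half-tablet note. If both meant 25 mg from the same tablet, the note would have no purpose. Listing two periods at the same dose proves nothing by itself, because 100 mg also appears twice, for weeks 7-10 and weeks 11-16.

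**The case against.** The best defence is that the intent can be recovered. Half a tablet followed by a plain 25 mg reads naturally as half of a 25 mg tablet and then a whole one, and the halving pattern supports that. Reading B needs a 50 mg tablet that the protocol never mentions. An investigator controls dosing, a study doctor signs every prescription, clinicians check for rash at each visit, and treatment-emergent rash is handled as a serious adverse event. These measures lower the risk and count in the plan's favour. None of them states a dose, however, and the rash checks detect harm after the first dose has been taken. The number printed is still 25 mg.

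The defence is also right about how far the point can be pressed. Four stronger readings are tempting, and the documents do not support them:

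- *The protocol contradicts itself, or orders an unreduced dose.* A 50 mg tablet would reconcile the line, and no strength is given. It is an ambiguity.
- *12.5 mg is the protocol's dose.* That is inferred from a pattern. The outside guidance is cited without numbers.
- *Many participants are exposed in the period of highest risk.* Valproate is one of several options for bipolar I, bipolar II participants may take lamotrigine alone, and no count is given. The protocol places almost all life-threatening rashes 2 to 8 weeks after starting, which meets the unclear step only at its boundary.
- *The risk of 1 in 100 quoted for the combination measures the harm.* That figure is a background risk for taking both drugs, not the excess from a doubled starting dose.

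**Conclusion.** The point stands as a dosing inconsistency that affects safety. It is not a criticism of the design. The weeks 1-2 dose with valproate has two possible meanings, 12.5 mg or 25 mg daily, and the higher equals the full starting dose without valproate. The internal evidence favours 12.5 mg but does not settle it.

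The size is a possible two-fold starting dose confined to two weeks, in lamotrigine-arm participants who take valproate. The documents give neither their number nor the risk of rash by starting dose, so no excess risk can be computed. The link to harm rests on the protocol's own list, which calls these causes suggested and potential. No effect on analysis or power is claimed. The line still needs correcting, because it sets a dose that will be acted on wherever valproate is the background treatment.

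**What to change.** Ask the sponsor to confirm the intended dose. Then rewrite Study Medication item 5 with one dose in mg and the tablet strength. The likely wording is: *lamotrigine 12.5 mg daily (half of a 25 mg tablet) for weeks 1-2, 25 mg daily for weeks 3-4*, with the later steps unchanged. If the sponsor confirms 25 mg instead, item 5 should say so, name the tablet strength, and explain why the first step is not reduced for valproate.

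The cost is one confirmation, one amended line, and a notice to sites and pharmacy. No procedure or data collection is added.

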**Fluoxetine:**

Given the dearth of FDA approved treatments for bipolar depression, antidepressants (FDA approved for unipolar major depression) are invariably prescribed; up to 49.8% of bipolar patients have reported initial treatment with an antidepressant (Baldessarini et al., 2007). In combination with an atypical antipsychotic (olanzapine), fluoxetine has been FDA approved for the treatment of bipolar depression. It is the only antidepressant combined with a mood-stabilizer that is FDA approved for bipolar depression. In the study by Tohen et al (2003), olanzapine plus fluoxetine combination (n=86) was associated with a significant reduction of depressive symptoms in comparison to olanzapine monotherapy (n=370) and placebo (n=377). In a study by Cohn et al (1989), fluoxetine monotherapy (n=30) was reported to be more efficacious than imipramine (n=30) and placebo (n=29) in patients with bipolar depression; furthermore, there were no cases of antidepressant induced mania among fluoxetine treated patients. Finally, in two studies by Amsterdam et al (2005, 2010), fluoxetine monotherapy (n=37 and n=28) was reported to have equal efficacy and no increased risk of antidepressant induced mania compared to lithium (n=26) or placebo (n=27), in the acute and prophylactic treatment of bipolar II depression.

There are no comparative effectiveness trials of fluoxetine in unipolar depression vs bipolar depression, however the evidence shows efficacy and safety of fluoxetine for bipolar depression,

**Lamotrigine:**

Lamotrigine is FDA approved for the maintenance phase or relapse prevention of bipolar I disorder and there is increasing impression of efficacy in acute bipolar depression. Geddes et al (2009) reported that bipolar depressed participants treated with lamotrigine were more likely to respond to treatment than those treated with placebo on both HAM-D (RR=1.27, 95% CI=1.09-1.47, Heterogeneity  $\chi^2=1.80$  (df=4)  $p=0.772$ , Test of RR=1:  $z=3.13$   $p=0.002$ ) and MADRS (RR=1.22, 95% CI=1.06-1.41, Heterogeneity  $\chi^2=3.12$  (df = 4)  $p=0.538$ , test of RR=1:  $z=2.80$   $p=0.005$ ). In a study by van der Loos et al (2009; n=124), the use of lamotrigine as an adjunctive treatment for patients already on lithium treatment was shown to significantly decrease depressive symptoms compared to placebo. Regarding safety of lamotrigine in bipolar depression, no AEs had greater than 5% frequency in the lamotrigine-treated groups, and no AE occurred at least twice as frequently in the lamotrigine-treated groups (n=1256) as in the placebo groups", as shown in a recent meta-analysis (Seo HJ et al, 2011). In the same study, it was shown that nonfatal serious AEs were observed in 6.6% of the lamotrigine treatment group and 7.2% of the placebo group. In general, lamotrigine has been considered a safe medication when used as a treatment for bipolar depression. The PI of this protocol has an ongoing IRB approved protocol looking at imaging markers of lamotrigine response which did not require an IND exception.

**Risk mitigation plans:**

As there will be 3 adverse events of special interest for this study (skin rash, antidepressant-induced mania and suicidal ideation), to mitigate those risks there will be a special monitoring and tracking of those events. At each visit, patients will be assessed for treatment-emergent manic symptoms using the BISS scale, for suicidality using the BISS and C-SSRS scales also and all study clinician will assess for skin rash at each visit. In addition, for populations where the risk of antidepressant-induced mania has been shown to be higher than placebo (bipolar I disorder), patients who are randomized to fluoxetine will be required to stay on a mood-stabilizer during the course of the study to decrease the likelihood of a treatment-emergent mania. A Data Safety and Monitoring Board will review safety data every 6 months.

Date and time of last dose of study medication will be gathered at the 1, 2, 4, 8, 12, and 16 week visits. To ensure compliance with the protocol, subject will bring in their medications at each visit for medication counts. The importance of medication compliance will also be discussed with the subject. To study medication compliance and pharmacokinetic pharmacogenomics blood levels of medication will be measured at week 16.

If participants are on current medications and are otherwise candidates for the study, their primary clinician will be contacted as to the relative merits of enrolling in the study. If it is clinically indicated (i.e. medicines are not helping optimally), the subject will be tapered off all psychotropic medications.

2. Adjunctive and concurrent medications. Adjunctive treatments are those used to manage transient associated symptoms (e.g., insomnia) or transient or longer-term medication side effects (e.g., sexual dysfunction). Adjunctive treatments that are not used to treat depression may be taken during the study. However, drugs in the exclusion criteria for this study may not be used as adjunctive therapies. Participants can participate in the study while receiving concurrent medications for general medical conditions as long as there is no contraindication to their use while taking fluoxetine.

3. Drug efficacy phenotype evaluation. The change in CGI-BP will constitute the major research outcome measure used to assess drug response phenotype because it is widely used in psychiatric research, making it possible to perform comparisons with other studies; it also provides a continuous phenotype of response to treatment. However, the BISS assessment will be administered at each research visit (week 0, enrollment week 1, 2, 4, 8, 12, and 16), and the results of these scales will also be examined and analyzed as more specific phenotypes by item and continuous phenotypes of response of depressive and emergence of manic/hypomanic symptoms. The instruments will be assessed by a SC assisted by the PI/CoPI.

5. Drug adverse event to treatment phenotype evaluation. Drug side effects will be recorded as expressed by the participant.

6. Gene selection. Gene pathways will be selected for inclusion in the genotyping studies based on the characteristics of the probe drugs', lamotrigine or fluoxetine, as explained above in the introduction. Genes encoding proteins that metabolize or transport lamotrigine/fluoxetine or participate in CNS glutamate, calcium or monoamine neurotransmitter systems (especially 5-HT neurotransmission) are candidates for variation that might influence drug response. Genes encoding 5-HT, glutamate, catecholamine and calcium biosynthetic, metabolic, storage, reuptake, receptor and intracellular signaling proteins, plus lamotrigine/fluoxetine metabolizing and transport proteins will be potentially chosen for genotyping. These gene pathways are and will be identified as described in preceding and future pharmacogenomic literature. The genomic and pharmacogenomics study of bipolar disorder and its medication is continuously being enriched; the gene selection of the present study will evolve to reflect what is deemed scientifically relevant and innovative by current literature.

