**Exclusion Criteria:**

1. Inability or unwilling to provide informed consent.
2. Inability to understand English.
3. Actively suicidal participants at screening or enrollment visit defined as a response of 3 or 4 on question 4 of the Bipolar Inventory of Symptoms Scale (BISS).
4. Active delusions or hallucinations defined as a score of 3 or 4 on the BISS question 40 (persecutory ideas) or 41 (delusions or hallucinations).
5. Impaired insight as defined as a score of 3 or 4 on BISS question 42 (insight).
6. Hypomania defined by a BISS manic subscore of  $\geq 15$ .
7. Actively suicidal patients as defined by any of the following responses to questions from the C-SSRS: "Yes" response to questions 4, "Yes" response to question 5, "Yes" response to questions 1, 2 or 3 with scores of 4 or 5 in any of the intensity of ideation items within the last week. Axis I or II comorbidity that by referring mental health professional and/or study psychiatrist is primary need of treatment (This will be assessed by the site principal investigator, who has  $>10$  years clinical experience with this population. Hospital discharge summaries and outpatient medical records may be reviewed (i.e. adequate trials of mood stabilizing treatments with minimal to no response, prominent self-injurious behavior in the absence of significant mood symptomatology, or atypical cycle patterns) to make this decision).
8. Pregnant participants.
9. Unwilling or unable to taper any current antidepressant therapy.
10. Participants currently breastfeeding.
11. Female not practicing a reliable form of birth control (condom, IUD, depo injection)
12. Due to lamotrigine pharmacokinetics, female subjects wishing to commence oral contraceptive therapy (OCT) within 3 months of enrollment date or anticipate discontinuing OCT during study (stable oral contraceptive therapy exception).
13. History of active substance abuse disorder within the last 3 months (other than caffeine or cannabis).
14. Participants with medical contraindications that preclude lamotrigine or fluoxetine treatment.
15. History of severe adverse reaction to lamotrigine and/or fluoxetine.
16. Current carbamazepine or oxcarbazepine treatment
17. Unstable active medical illness.

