Selected participants may be asked to have their SCID interview audio/videotaped. These participants would be selected by the investigator and would sign a separate consent allowing permission to be taped. This tape would only be identified with the participant's study identifier and kept in a locked file. The purpose of these tapes would be to be used for inter rater reliability and quality assurance across the multi-site project.

If a participant fulfills all inclusion and exclusion criteria and he/she is not on an antidepressant at the screening visit, can continue directly to the enrollment visit and be randomized.

If the participant was on an antidepressant at the time of the screening visit, he/she is willing to discontinue it and it would be clinically reasonable to stop it, then the antidepressant will be tapered off in 1 week. The participant will have to be at least 7 days completely off the antidepressant before randomization. Then, the total number of days from screening to enrollment for these participants will be 14 days.

Patients enrolling in FLAME will also be given the option to participate in a separate study called 1H-MR Spectroscopy Before and After Treatment with Lamotrigine or Fluoxetine in Bipolar Depression (IRB 13-003660). This study is designed to only recruit subjects who participate in FLAME. This study will be conducted in tandem with FLAME.

Enrollment/baseline/randomization visit (could be at the same day of screening visit)

After consent is obtained and eligibility has been confirmed (inclusion/exclusion criteria; SCID, questionnaire ratings and blood drawn), RAVE® randomization case report form (CRF) will be submitted. Randomization will be done using blocking (blocks of 6 participants), and by study site with RAVE® (License) randomization tool. Block randomization will be utilized to assure balance between the 2 treatment arms. BPI disorder participants, who are randomized to fluoxetine and were not receiving any mood stabilizers at the enrollment visit, will be started on a conventional mood stabilizer just after randomization. These participants should be on a mood stabilizer for at least 7 days before starting study medication.

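### The conditional psychotropic taper makes no exception for the antimanic treatment that inclusion criterion 4 requires, and the mood-stabiliser start rule for bipolar I covers only the fluoxetine arm

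*Combined protocol and SAP*

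**What the plan says.** Five parts of the combined protocol and SAP bear on this.

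- **Risk mitigation plans.** For candidates on current medication, the primary clinician is contacted about enrolment, and then: "If it is clinically indicated (i.e. medicines are not helping optimally), the subject will be tapered off all psychotropic medications". The same section requires bipolar I participants randomised to fluoxetine to remain on a mood stabiliser during the study.
- **Inclusion Criteria, item 4.** "Bipolar I participants must be on conventional mood stabilizing treatment", with lithium, valproate/divalproex and atypical antipsychotics as the accepted agents. "Participants with Schizoaffective Bipolar Disorder must be on an atypical antipsychotic". "Participants with bipolar II disorder may pursue the FLAME Study as monotherapy".
- **Antidepressant taper.** Exclusion Criteria item 9 and the Screening visit text deal with antidepressants only, with timing: one week of taper, then at least 7 days off before randomisation. Exclusion item 16 separately bars "Current carbamazepine or oxcarbazepine treatment".
- **Enrollment/baseline/randomization visit.** Randomisation follows confirmation of eligibility. The text nevertheless provides for "BPI disorder participants, who are randomized to fluoxetine and were not receiving any mood stabilizers at the enrollment visit", who are then started on one. "These participants should be on a mood stabilizer for at least 7 days before starting study medication". No such provision is written for lamotrigine or for schizoaffective participants.
- **Data & Safety Monitoring Plan.** Participants must satisfy every inclusion criterion, and the study coordinator and principal investigator check this before study drug begins.

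**The concern.** The taper sentence refers to all psychotropics and sits in the section meant to reduce risk, yet the drugs it covers include the ones item 4 makes a condition of entry. Its trigger is also wide: every candidate must be currently depressed, so many who arrive on medication could be described as not optimally helped.

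At stake is protection against mania while study treatment is started. The protocol makes treatment-emergent mania a reason for discontinuation and handles it as a serious adverse event. BISS ratings at visits detect mania once it appears; they do not prevent it. An eligibility check can stop enrolment, but it does not restore treatment already withdrawn.

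There is also an analytic cost. Antidepressant-induced mania is one of the adverse-event phenotypes, and concomitant medication is a planned covariate. If sites act on different sentences, similar patients will carry different background treatment for reasons unrelated to their illness.

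**Working it through.** The plan gives no figure to reproduce, and no alpha, power or sample-size calculation applies. The check sets the rules side by side.

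**Step 1. Scope of the taper rules.** Exclusion item 9 and the Screening visit text taper antidepressants only. The sentence under Risk mitigation plans tapers all psychotropics. It is the only rule of that breadth, and it gives no duration, off-drug interval or re-check.

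**Step 2. Taper against item 4.** Item 4 covers three diagnoses. Bipolar II may enter on monotherapy, so a full taper is compatible with it. That leaves 3 − 1 = 2 diagnoses, bipolar I and schizoaffective, in which a full taper removes a required treatment.

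**Step 3. What is written for a candidate with no cover at enrolment.**

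| Diagnosis | Arm | Item 4 requires cover? | Rule to start cover? | Rule to stay on it? |
|---|---|---|---|---|
| Bipolar I | Fluoxetine | Yes | Yes, at least 7 days before study drug | Yes |
| Bipolar I | Lamotrigine | Yes | None | None |
| Schizoaffective | Either | Yes | None | None |
| Bipolar II | Either | No | Not needed | Not needed |

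Lamotrigine is not among the agents item 4 lists, so study drug does not itself satisfy the criterion.

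**Step 4. Does the eligibility check close the gap?** Applied strictly, yes: an uncovered bipolar I or schizoaffective candidate fails item 4 and should not start study drug. Three pieces of text weaken confidence in that:

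- The enrolment text puts randomisation after eligibility is confirmed, yet expects some bipolar I participants to be randomised on no mood stabiliser.
- The re-check after an antidepressant taper names the BISS, C-SSRS and CGI-BP, none of which records whether antimanic treatment is in place.
- Study Medication lists all three diagnoses and then gives a lamotrigine schedule headed "Dosing for adults as monotherapy or on lithium or antipsychotic", without confining monotherapy to bipolar II.

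**Step 5. Are the two gaps the same?** No. The enrolment text applies however a bipolar I participant came to be without a stabiliser. If the taper sentence were deleted, a bipolar I candidate who arrived untreated and drew lamotrigine would still have no start rule. Conversely, exempting only item 4 agents from the taper would not help a bipolar I candidate whose sole stabiliser is carbamazepine or oxcarbazepine: that drug has to go under exclusion item 16, and the candidate then reaches enrolment uncovered.

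**The case against.** The strongest defence is that the taper is conditional. It depends on clinical indication and follows contact with the primary clinician, who may judge that a mood stabiliser should stay. A poorly working agent can be withdrawn and another item 4 agent started before study drug. The detailed, timed procedure concerns antidepressants only, so the broad sentence may simply be loose drafting. Arm-specific cover may also be deliberate: the on-study requirement is tied to antidepressant-induced mania, and the protocol notes lamotrigine's maintenance approval in bipolar I.

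Much of this stands. A reader might infer that the taper and item 4 can never both be followed; the conditional wording and the possibility of a replacement agent do not support that. A reader might also infer that a tapered bipolar I participant on lamotrigine will spend the whole trial, 16 × 7 = 112 days, without cover. That requires the eligibility check to fail; 112 days is only the trial's length, not an estimate of exposure. Nor does the lamotrigine gap originate in the taper sentence.

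What the defence does not supply is a written exception, a rule that a withdrawn item 4 agent must be replaced, or a statement that uncovered lamotrigine is acceptable in bipolar I. If that last point is the intention, item 4 currently says the opposite.

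**Conclusion.** The concern holds in limited form. The taper sentence is broader than every other taper rule and makes no exception for treatment that item 4 requires in two of the three eligible diagnoses. Acting on it as written can remove required cover and make the candidate ineligible. Separately, the enrolment text has a start rule for one of the two bipolar I arms and none for the other, which matters if the eligibility check is not strictly applied.

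The counts of diagnoses and arms describe rules, not people. The documents give no breakdown by diagnosis, no taper rate and no number arriving untreated, so the number affected cannot be derived. The conclusion rests on reading the taper sentence literally and on item 4 applying in both arms, as it is written. This should be corrected as a matter of safety and consistency between sites; it does not undermine the trial's design.

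**What to change.** - **Risk mitigation plans.** Limit the taper to antidepressants, excluded drugs and other psychotropics that item 4 does not require. State that item 4 treatment is kept, or is replaced by another item 4 agent before study drug if the current stabiliser is ineffective, not tolerated or excluded (for example carbamazepine or oxcarbazepine).
- **Enrollment/baseline/randomization visit.** Bring the start rule into line with item 4: confirm cover before study drug for bipolar I in both arms and for schizoaffective participants.
- **Alternative.** If lamotrigine without cover is intended in bipolar I, amend item 4 to say so.

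Bipolar II needs no change.

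The cost is a short amendment in two places. Some candidates, in a number the documents do not give, would start or switch a mood stabiliser before study drug, which may delay the first dose. No new dosing schedule is needed: Study Medication already covers lamotrigine with lithium or an antipsychotic, and has a slower titration with valproate. The protocol puts the serious rash risk for lamotrigine with divalproex at 1 in 100, which should weigh in the choice of replacement agent, but item 4 already admits that combination.
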